5.3.3 Safety Assessment

Safety will be assessed by tabulation of Adverse Events and will be presented with descriptive statistics at Baseline and each treatment arm. Adverse events will be summarized by treatment group. Treatment groups will be compared with respect to the incidence of each type of adverse event observed.

The n, mean and standard deviation of serum potassium and glucose, SBP/DBP, HR and ECG readings will be summarized per treatment arm by time of testing. The frequency count and percentage of whether any significant changes in physical exam, ECG and Lab results since screening visit will be reported at the end of study.

Any early termination will be listed with primary reasons per treatment arm as part of the safety assessment.

5.4 INTERIM ANALYSES

No interim analyses are planned for this study.

5.5 DATA QUALITY ASSURANCE

5.5.1 Data Input

Study data is entered into e-CRF (Electronic Case Report Form) by the site personnel. The e-CRF data management system is a web based application that is used to manage study data. The e-CRF data management system is validated to comply with FDA 21 CFR Part 11.

5.5.2 Data Quality Assurance and Monitoring

The trial will be monitored according to current Amphastar Standard Operating Procedures (SOPs).

The sponsor site monitors will monitor investigational activities for the purpose of subject safety, study compliance to applicable regulatory guidelines, and study source data for quality and integrity.

The review of the e-CRF study data entries is also conducted by the sponsor site monitors, to ensure that CRF data is accurate and traceable to the reliable study source. The Investigators will permit Amphastar authorized monitors to access the subject source documents, clinical supplies dispensing and storage area and study documentation as frequently as necessary and agrees to assist the site monitors with their activities. In addition, the e-CRF data is also reviewed remotely by authorized personnel (Data Manager and safety Monitors) for data completeness and format. The Investigator will review the eCRF; provide missing or corrected data and e-sign the eCRF at the close out of the study. Personal or subject identifying information will be treated as confidential and will NOT be publicly accessible. The trial information may be reviewed by regulatory authorities or independent QA auditors. The study site may be inspected during or after completion of the study. The Investigators agree to allow inspectors from regulatory agencies to have access to all study records, including subject source documents and eCRF study data. By participating in this study, the

Investigators agree to these requirements and will assist the inspectors in their duties.

5.5.3 PK Samples Collected Out of the Sampling Window Defined by the Protocol

Being out of the pre-specified sampling window is one of the commonly existing protocol deviations. This type of protocol deviation may be flagged or excluded, as discussed below.

Assuming three (3) PK sampling time points are t_{j-1} , t_j , and t_{j+1} respectively, as demonstrated in Figure 2 below.

The time gap between PK sampling time points $j-1$ & j , denoted as g_{j-1} , is:

$$g_{j-1} = t_j - t_{j-1} \quad (12)$$

The time gap between PK sampling time points j & $j+1$, denoted as g_j , is

$$g_j = t_{j+1} - t_j \quad (13)$$

The PK sampling window defined in protocol for sampling point t_j is $t_j \pm w_j$. In case a PK sample at the time point j was collected out of the window, a “flag-allowance” for the PK sample, denoted as θ_j (%), can be assigned to determine to flag or to exclude the corresponding PK sample, i.e.

- If the actual PK sample is within $t_j \pm w_j (1+\theta)$, flag the PK sample;
- If the actual PK sample is out of $t_j \pm w_j (1+\theta)$, the PK sample will be excluded and treated as a missing data point.

[figure not shown]

Figure 2 Sampling Points, Window and Flag-Allowance

As a minimum requirement, sample at t_j should have no possibility to overlap with samples at t_{j-1} (the previous sample) or t_{j+1} (the next sample), thus the flag-allowance θ_j must meet the below two equations simultaneously:

$$w_j(1 + \theta_j) \leq \frac{g_{j-1}}{2} \quad (14)$$

$$w_j(1 + \theta_j) \leq \frac{g_j}{2} \quad (15)$$

From Eqs (14) & (15), one has the maximum flag-allowance will be

$$\theta_j \leq \min \left[\frac{g_{j-1}}{2w_j} - 1, \frac{g_j}{2w_j} - 1 \right] \quad (16)$$

The maximum allowed flag range, denoted as F_j can be obtained as:

$$\pm F_j = \pm \theta_j w_j \quad (17)$$

The safety coefficient, denoted as S_j , for an actually assigned flag-allowance, denoted f_j , can be obtained as:

$$S_j = \frac{F_j}{f_j} \times 100\% \quad (18)$$

It is expected that $S_j \geq 100\%$.

The suggested flag-allowances of out-of-sampling-window for PK samples in this study are listed in **Table 4** below.

Table 4 Flag-Allowances of Out-of-Sampling-Window for PK Samples

#	Sampling Plan			Calculation			Evaluation for out of window		
	Description	Time Gap g _j	w _j in	g _j /(2w _j)-1	θ _j	maximum Flag-Allowed F _j =θ _j w _j	proposed f _j NMT 25%w _j	Safety Coefficient S _j	Comments for f _j
0	C1: Baseline			-					
1	C2-C4 (Min. 1,2,3): 1 ± 0.5	1	0.5 min	0%	0%	0 min	0	-	no flag allowance
2	C5-C7 (Min. 5,7,9): 2 ± 1	2	1 min	0%	0%	0 min	0	-	ibid
3	C8-C11 (Min. 12, 15, 18, 21): 3 ± 1	3	1 min	50%	0%	0 min	0	-	ibid
4	C12-C13 (Min. 25,30): 5 ± 2	5	2 min	25%	25%	0.5 min	0.5	100%	
5	C14-C19 (Min. 40, 50, ...80, 90): 10 ± 5	10	5 min	0%	0%	0 min	0	-	no flag allowance
6	C20-C21 (hr. 2): 120 ± 10	30	10 min	50%	0%	0 min	0		ibid
7	C20-C21 (hr. 4): 120 ± 10	120	10 min	500%	50%	5 min	30	17%	
8	C22-C23 (hr. 6,8): 120 ± 15	120	15 min	300%	300%	45 min	45	100%	
9	C24-C26 (hr. 12, 18,24): 360 ± 20	360	20 min	800%	300%	60 min	40	150%	

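### SAP Table 4's 4 h row fails the SAP's own check, and the out-of-window rule discards assayed PK samples that could be kept at their actual draw times

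*SAP*

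**What the plan says.** SAP 5.5.3 opens by stating: "Being out of the pre-specified sampling window is one of the commonly existing protocol deviations". It then introduces θ, a flag-allowance that "can be assigned to determine to flag or to exclude the corresponding PK sample". A sample within w(1+θ) of its scheduled time, where w is the protocol window, is flagged. Beyond that, "the PK sample will be excluded and treated as a missing data point".

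The section defines two further quantities. F = θ × w is "The maximum allowed flag range". S = F/f is the safety coefficient "for an actually assigned flag-allowance", f, and S is expected to be at least 100%. Eqs. (14) to (16) cap θ so that a sample cannot overlap its neighbours. Table 4 lists the values, with the 4 h sample in the row "C20-C21 (hr. 4): 120 ± 10". Its heading for f sets a maximum of 25% of w, and the allowances are called suggested.

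Other sections that bear on this:
- SAP 5.2.1: missing points of evaluable subjects are interpolated.
- SAP 4.1.1: Cmax is the largest experimental value. The t_i used for Cmax and AUC is described only as the time of the sampling point, without saying actual or scheduled.
- SAP 5.1.1: the primary (per-protocol) population requires evaluability for all treatments. Items (5), (6) and (7) each require four of five named points, for Treatments A, B and C respectively.

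**The concern.** There are two separate issues.

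First, the 4 h row, "C20-C21 (hr. 4): 120 ± 10", carries a printed S of 17% without comment. A 4 h sample drawn 20 min late is excluded if θ governs and flagged if f governs.

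Second, the rule can only be applied to a sample whose actual draw time is known. Such a sample has a measured concentration at a known time, and the trapezoidal formula in Eq. (2) accepts unequal intervals. Deleting it and interpolating in its place gives up information on primary endpoints. Many of the affected times are the ones that decide evaluability. At stake are a one-directional error in each treatment's Cmax and avoidable loss of subjects from a primary population with a target of 24.

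**Working it through.** **Table 4 check.** Inputs are w, θ and f as printed. Times are in minutes.

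| Sample | w | θ | F = θw | f | S = F/f | f/w | w(1+θ) | w + f |
|---|---|---|---|---|---|---|---|---|
| 25, 30 min | 2 | 25% | 0.5 | 0.5 | 100% | 25% | 2.5 | 2.5 |
| 4 h | 10 | 50% | 5 | 30 | 17% | 300% | 15 | 40 |
| 6, 8 h | 15 | 300% | 45 | 45 | 100% | 300% | 60 | 60 |
| 12, 18, 24 h | 20 | 300% | 60 | 40 | 150% | 200% | 80 | 60 |

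- The printed 17% is reproduced: 5/30 = 16.7%. The row therefore fails as computed; it is not a broken table cell.
- At 4 h, Eq. (16) allows θ up to 120/(2 × 10) − 1 = 500%. With f = 30, S reaches 100% once θ is 300% (F = 30). With θ = 50%, it requires f of at most 5.
- 25% of w is 2.5, 3.75 and 5 min in the last three rows, against f of 30, 45 and 40.
- At 25 min the previous sample is at 21 min, a gap of 4. Eq. (16) gives at most 4/(2 × 2) − 1 = 0%, but the table uses 25%. Eq. (14) fails, since 2 × 1.25 = 2.5 exceeds 4/2 = 2.

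**Zero-allowance times.** 1, 2, 3, 5, 7, 9, 12, 15, 18, 21 min (10) plus 40, 50, 60, 70, 80, 90, 120 min (7) = 17 of 25. Eq. (16) gives exactly 0% at 12 of these (1 to 9 min and 40 to 90 min). At the other five (12, 15, 18, 21 and 120 min) it permits 50%: 3/(2 × 1) − 1 and 30/(2 × 10) − 1. The table still sets 0% there, for example in row "C8-C11 (Min. 12, 15, 18, 21): 3 ± 1". The 17 times cover all five points of item (5), all five of item (6), and 40, 50 and 60 min of item (7).

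**Cmax.** The maximum over a subset cannot exceed the maximum over the full set. A value interpolated between two neighbours cannot exceed the larger of them, so imputation cannot restore a lost peak.

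**Evaluability (illustration).** The documents give no out-of-window rate. Assume independent exclusions with probability p per sample.
- One item fails if two or more of its five points are excluded: q = 1 − (1−p)^5 − 5p(1−p)^4 = 0.38%, 2.26%, 8.15% at p = 2%, 5%, 10%.
- Item (5) or (6) fails: 1 − (1−q)^2 = 0.8%, 4.5%, 15.6%.
- Times 24: about 0.2, 1.1 and 3.8 subjects.

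**Albuterol AUC (illustration).** Assume mono-exponential decline from 2 h with the 6 h half-life in Protocol 1.4, and trapezoids at 2, 4, 6, 8, 12, 18 and 24 h. Compare excluding a sample with keeping it at its actual time.
- Linear interpolation: that subject's 2 to 24 h AUC rises about 0.5% (4 h sample, 15 to 40 min off) or 2.5 to 3.0% (12 or 18 h sample, 60 to 80 min off). If one of 24 subjects is affected, the mean moves about 0.5/24 = 0.02% or 3.0/24 = 0.12%.
- Log-linear interpolation: the change is at most about 0.07% and 0.4% for that subject, mostly downward.
- A 24 h sample has no later neighbour to interpolate towards. Leaving out 18 to 24 h would cost that subject about 9% of the 2 to 24 h area.

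**The case against.** The strongest defence is that the rule is pre-specified and the same for every treatment, and that most zero allowances have a stated reason. That holds for 12 of the 17 times, so a reader should not infer that all 17 are arbitrary. But no-overlap is needed only to assign a sample to a scheduled time, as in the planned mean concentration-time curves. Cmax and AUC do not need it when actual times are used.

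On Table 4, f can be read as the working value and F as its ceiling. Row "C24-C26 (hr. 12, 18,24): 360 ± 20" is then coherent (F 60, f 40, S 150%) and should not be called an error. The 4 h row still fails under that reading, and the written exclusion rule uses θ, not f. A reader might also infer that the 4 h entry lets samples overlap. It does not: 10 + 30 = 40 min is below half the 120 min gap.

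Losses are partly handled elsewhere. Enrolment aims at 24 evaluable subjects, and SAP 5.1.2 analyses PK in the treated population. So it would be too strong to say that subjects are lost to all analysis: they leave the primary population. The treated-population analysis is supportive only, however, and SAP 5.2.2 contradicts it by excluding non-evaluable subjects from PK evaluation. Extra enrolment can restore numbers but cannot correct a lowered Cmax in a subject who stays evaluable.

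Finally, the SAP's remark that out-of-window draws are common is general and is not a rate for this study. The 2 to 10% range and independence are assumptions, and clustering of late draws within a visit would change the result. This stands.

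**Conclusion.** Table 4 is wrong as written at 4 h (S 17% against at least 100%; limit ±15 or ±40 min). It also breaks Eq. (14) at 25 min and exceeds its own 25% heading from 4 h onward. Alone this is a small correction: it touches late samples and the 25 min point, and the 4 h discrepancy is unlikely to affect Cmax.

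The exclusion rule is the more important point, as a cheap improvement rather than an arithmetic error. It can lower a treatment's Cmax and never raise it, and two exclusions within one of items (5) to (7) remove the subject from the primary population for all three treatments. Its real size is unknown because no out-of-window rate is given; the illustration rests on assumed, independent rates. A reader might infer a material bias in mean albuterol AUC. The documents do not support that: with one of 24 subjects affected at 4, 12 or 18 h, the mean moves about 0.1% or less, and even that depends on an interpolation method the SAP does not specify.

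**What to change.** For the exclusion rule:
- Define t_i as actual elapsed time since dosing.
- Compute Cmax, tmax and AUC from every assayed sample at its actual time.
- Flag out-of-window samples and count them as available for evaluability.
- Exclude a sample only when its actual time cannot be established.
- As a consequence, state how the albuterol AUC is brought to 24 h when the last draw is not exactly at 24 h.

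The downside is that a kept sample may fall nearer to a neighbouring scheduled time. Keep the no-overlap rule only for assigning samples to nominal times in the mean concentration-time plots.

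If Table 4 is kept:
- State whether w(1+θ) or w + f governs exclusion.
- Reconcile θ, F and f at 4 h so that S is at least 100%. One example is θ 300% with F = f = 30 min, within the 500% ceiling.
- Correct the 25 min entry.
- Apply or remove the 25% heading.

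θ × w and f need not be equal at 12 to 24 h. The cost is SAP wording and a few table entries. Draw times are already needed to apply the existing rule, so no new data are required.

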5.5.4 Database and Computer Programs for Statistical Analysis

A specialized trial-specific database is designed to capture data in such a way that it facilitates reporting and analysis, i.e. minimal data manipulation and programming to complete the analysis.

The data capture and report system is fully tested and validated. The system is demonstrated to be accurate, reproducible and secure.

The computer programs used for statistical analysis will be validated.

Attachment:

Template of Statistical Analysis Output for Clinical Study Protocol No. API-E004-CL-I
(Available Upon Request)
